## 1. Glossary and abbreviations

[figure not shown]
AE	Adverse Event
ALS	Advanced Life Support
APP	Advanced Paramedic Practitioner
CI	Chief Investigator
CPR	Cardiopulmonary resuscitation
CRF	Case Record Form
CTU	Clinical Trials Unit
CVCTU	Cardiovascular Clinical Trials Unit
DSMC	Data Safety and Monitoring Committee
ECMO	Extra-Corporeal Membrane Oxygenation
ECPR	Extracorporeal Cardiopulmonary Resuscitation
ED	Emergency Department
FIM	Functional Independence Measure
GCP	Good Clinical Practice
ICU	Intensive Care Unit
ISF	Investigator Site File
JRMO	Joint Research Management Office (Barts Health/QMUL)
LAS	London Ambulance Service
NHS	National Health Service
NIMP	Non-investigational Medicinal Product
OHCA	Out-of-hospital Cardiac Arrest
PEA	Pulseless electrical activity
PI	Principal Investigator
REC	Research Ethics Committee
REDCap	Research Electronic Data Capture
ROSC	Return of spontaneous circulation
SAE	Serious adverse event
SOP	Standard Operating Procedure
SPC	Summary of Product Characteristics
TMF	Trial Master File
TOR	Terms of reference
TSC	Trial Steering Committee
UK	United Kingdom
VA-ECMO	Veno-arterial-ECMO
VF	Ventricular fibrillation
VT	Ventricular tachycardia

**Principal Investigator Name:** **[name]**

**Signature:** 

**Date:** **02 March 2022**

### 3. Summary and synopsis

Short Title	Sub30
Methodology	Feasibility study of a complex intervention
Research Sites	Barts Health NHS Trust London Ambulance Service NHS Trust
Objective/Aims	To establish whether a pre-hospital advanced physician/ paramedic cardiac arrest team that is ECMO capable can establish ECMO flow within 30 minutes of collapse
Number of participants	6 patients who are cannulated for ECMO
Inclusion and exclusion criteria	
Male and female patients with a known or visible age of 18 to 65 years who:
 
 
have a witnessed out-of-hospital cardiac arrest
 
a presumed cardiac aetiology to their cardiac arrest
 
receive bystander chest compressions within 3 minutes
 
remain in cardiac arrest at 20 minutes following collapse or fail to sustain ROSC in the pre-hospital setting
 
 
The following patients will not be suitable for ECMO:
 
 
Identified as or visibly less than 18 years or greater than 65 years
 
Known or visible advanced pregnancy (when resuscitative hysterotomy should be performed)
 
Evidence from others present at the scene or patient examination that ECMO unlikely to benefit patient (e.g. advanced frailty, advanced malignancy, ...).
 
No signs of life (physical movement or breathing) AND evidence of ineffective chest compressions suggested by: 
 
Absence of electrical activity OR
 
End tidal carbon dioxide level of less than 1.3 kPa (10 mmHg)
 
 
 
 
Out-of-hospital cardiac arrest encompasses both those who arrest prior to the emergency services being called and those who are witnessed to arrest by the emergency services. For the purpose of this study patients who suffer their first cardiac arrest whilst in transit to hospital will not be included.

Statistical methodology and analysis	
Descriptive statistics will be presented summarising the process and outcomes of the six patients.
 
Outcomes will be compared to other patients who were managed by London Ambulance Service on non-study days. Statistical matching to patients cared for concurrently with the study period will utilise a priori defined factors that may be associated with likely suitability for ECPR. Statistical matching will be individual, propensity score based and GenMatch guided.

Proposed start date	01 June 2019
Proposed end date	31 December 2022
Study duration	3 years 7 months

## 4. Introduction

### 4.1 Out of hospital cardiac arrest – the healthcare need

In England, 91% of patients with out-of-hospital cardiac arrest died before leaving hospital in 2015 [1]. Within London, the London Ambulance Service (LAS) attended 10,116 out-of-hospital cardiac arrests (OHCA) in 2015/16 and attempted resuscitation in 4,389. Overall mortality was 91% for those in whom resuscitation is attempted [2]. Survival rates remain low despite improved bystander cardiopulmonary resuscitation (CPR), improved access to defibrillators, the introduction of automated compression devices and the introduction of advanced paramedic practitioners. Even among the subset most likely to survive (“Utstein comparator group” – bystander witnessed cardiac arrests with a shockable rhythm), 35.5% (199/560 in 2015/2016) of patients failed to achieve return of circulation and the overall mortality was 68.5% (371/542). The mortality for those patients with witnessed cardiac arrests but in a non-shockable rhythm was 97.5% (3,353/3,440).

### 4.2 Rationale for pre-hospital ECPR

#### 4.2.1 ECPR may improve outcome in refractory cardiac arrest

Poor survival from out of hospital cardiac arrest relates to an irreversible decline in cardiac function and/or ischaemic injury to the rest of the body, particularly the brain.

In 2015/16, 70% of all cases and 36% of the Utstein comparator group failed to achieve and sustain a return of a spontaneous circulation (ROSC) [2]. Failure to achieve sustained ROSC is a consequence of the precipitating pathology, insufficient coronary perfusion pressure generated by external chest compressions [3], significant cardiac dysfunction during transient ROSC, and the cardiac contusion from prolonged CPR. Failed or delayed ROSC delays treatment at the heart attack centre or Emergency Department (ED), and prolongs the “low blood flow” state - external chest compressions only generate a flow of  $\sim 0.6 \text{ L} \cdot \text{min}^{-1} \cdot \text{m}^{-2}$ , less than one-third of normal cardiac output [4]. This “low flow” state perpetuates organ ischaemia multi-organ failure and hypoxic brain injury - the leading causes of death in the two thirds of patients who die in hospital despite achieving ROSC.

Veno-arterial Extra-Corporeal Membrane Oxygenation (VA-ECMO) is a supportive technique that provides an effective circulation of oxygenated blood, over  $2 \text{ L} \cdot \text{min}^{-1} \cdot \text{m}^{-2}$  – far superior to external cardiac massage even with mechanical devices. VA-ECMO is performed by inserting a cannula into a large vein to all blood to be pumped from the patient through a membrane oxygenator (that removes carbon dioxide and adds oxygen) and then back to the patient via another cannula inserted into an artery. In this way, it supports both the heart and lungs, limiting organ ischaemia and allowing time for the definitive treatment at the heart attack centre. Moreover, VA-ECMO favourably influences myocardial oxygenation by enhancing coronary perfusion through an increased mean arterial pressure and reduced ventricular filling pressures coupled with a normalisation of acid-base abnormalities and often a reduction in cardiac work. Excessive mean arterial pressures may increase cardiac work and are avoided. This may limit on-going cardiac damage and is an emerging concept (“door to unloading time”) in the management of ST elevation myocardial infarction complicated by cardiogenic shock [5].

VA-ECMO is employed in a variety of clinical settings, but when used in cardiac arrest is termed Extracorporeal Cardio-Pulmonary Resuscitation (ECPR). The use of ECPR for in-hospital cardiac arrest is associated with a stepwise improvement in survival to hospital discharge depending on how rapidly ECPR is established: 40-50% for ECPR within 30 minutes of collapse, 30% for ECPR within 30-60 minutes, and 18% for ECPR beyond 60 minutes [6]. ECPR has also been used in out of hospital cardiac arrest, but is typically instituted in the ED. Transporting the patient to hospital delays ECPR, and the reported survival rates are typically lower at around 17% [7]. A recent case series published survival to discharge rates as high as 54% in a mix of in- and out- of hospital cardiac arrest patients, but the average time in survivors from collapse to ECPR was 40 minutes [8].

ECPR has never been investigated in randomised controlled trial.

#### **4.2.2 Pre-hospital institution of ECPR may be the best model of care**

Time to establish an adequate circulation is critical both in ECPR and conventionally managed cardiac arrest [6, 9-12]. The time taken to package and transport patients, after the required minimum of 20 minutes of advanced life support (ALS) on scene following OHCA, means that the earliest it is possible to institute ECPR in heart attack centres and EDs is approximately 60 minutes after arrest, the time at which survival starts to fall significantly. Pre-hospital ECPR instituted where the patient suffers a cardiac arrest may reduce this time interval.

The technical feasibility of pre-hospital ECPR has been demonstrated [13-16]. The logistic challenges of delivering a complex medical intervention in the pre-hospital setting are significant. They include identifying and reaching appropriate patients as soon as possible after their cardiac arrest, establishing a sterile field, accessing femoral veins and arteries during active resuscitation attempts, and managing a pre-hospital scene with all the potential environmental challenges.

The Parisian experience with pre-hospital ECPR is an excellent model to illustrate potential pitfalls. When pre-hospital ECPR was first introduced in Paris, the mean interval between collapse and ECPR was 79 minutes [15]. The ECPR team acted as a secondary response, deployed only after initial on-scene assessment by the primary responders, and mandatory conventional resuscitation for 30 minutes. Not surprisingly, these delays were associated with poor outcomes. Since then, they have refined their eligibility criteria and focused on faster dispatch to the scene. These modifications have translated into both shorter collapse-to-ECPR intervals and significantly improving clinical outcomes [17].

#### **4.3 Current UK clinical practice for OHCA**

Most ambulance services in England follow the European Resuscitation Council guidelines for pre-hospital resuscitation [18], which advise at least 20 minutes of CPR for all attempted resuscitations. If there is failure to achieve ROSC and the cardiac rhythm is asystole, then the resuscitation is terminated, typically. Resuscitation may also be stopped if the cardiac rhythm is pulseless electrical activity (PEA) after discussion with a clinical support desk. If the rhythm is refractory ventricular fibrillation/tachycardia (VF/VT), the patient will be transported with on-going CPR to the nearest emergency department or heart attack centre.

Hospital based ECPR is provided in a few EDs and heart attack centres throughout England on an ad-hoc, case-by-case basis. The UK Resuscitation Council 2015 guidelines recommend that ECPR should be considered as a rescue therapy for select patients in whom initial ALS techniques are unsuccessful [19]. There is no national protocol for its use and it has never been performed in a pre-hospital setting in the UK.

#### **4.4 Other current and planned studies of ECPR in patients suffering OHCA**

There are six other potential studies examining ECPR in patients suffering OHCA. These are summarised in Table 1. Indeed, a panel of experts recommended a trial of pre-hospital ECMO as a key study to undertake in the next 10 years [20].

The RECA study (Regensburg ECLS for Cardiac Arrest) aims to implement pre-hospital ECPR in patients between 18 and 65 years with witnessed cardiac arrests, of presumed cardiac aetiology (as assumed with a presenting rhythm of VF or VT) who receive bystander/healthcare worker CPR within 5-10 minutes. It is a single centre study run by the Universitätsklinikum Regensburg. The team is being dispatched via the integrated command centre in Regensburg at the same time as the primary response team. The study is not officially registered on any international database and its current status is not known.

ACPAR2 (A Comparative study between a Pre-hospital and in hospital Circulatory support strategy [ECMO] in refractory cardiac ARrest; clinicaltrials.gov reference: NCT02527031) is a randomised controlled trial being run by the Service d'Aide Médicale Urgent (SAMU) in Paris. It began recruiting in March 2016. It aims to recruit 210 patients, aged between 18 and 65 years, who remain in medical cardiac arrest at 20 minutes. It aims to achieve VA-ECMO between 20 and 30 minutes and compare these to patients transferred at 30 minutes to the hospital for ECPR.

Patient exclusions include those who have more than five minutes of collapse without CPR and those with an end tidal carbon dioxide level of less than 10 mmHg (1.3 kPa). It is powered to detect an increase in survival without severe neurological dysfunction from 5 to 20%.

The CHEER3 study from the Alfred Hospital in Melbourne is being planned and aims to commence ECMO cannulation at 30 minutes and aiming to achieve blood flow by 45 minutes using percutaneous cannulation.

EROCA (ECPR for Refractor Out-of-hospital Cardiac Arrest; clinicaltrials.gov reference: NCT03065647) is currently in set up and run by the University of Michigan. It aims to enrol 30 patients over 18 months and compare conventional CPR against ECPR following expedited transfer to hospital with mechanical CPR for ECPR. Expedited transfer commences after the initial cardiac rhythm analysis and shock (if indicated). The primary outcomes are the times to arrival in the ED and ECPR commencing. Target times are arrival at hospital within 30 minutes and an additional 30 minutes to achieve ECPR.

ECPB4OHCA (Emergency Cardiopulmonary Bypass for Cardiac Arrest; clinicaltrials.gov reference: NCT01605409) is a single centre study being undertaken in Vienna. The study aims to randomise 40 patients, aged between 18 and 75 years, to receive conventional CPR or ECPR. In the ECPR group expedited transfer to the hospital is initiated following 15 minutes of standard ALS. The primary outcome is the rate of sustained restoration of the circulation. The study commenced in November 2014.

Prague OHCA study (clinicaltrials.gov reference: NCT01511666) is being undertaken by the Charles University, Prague. Patients, aged 18 to 65 years, suffering witnessed OHCA are randomised to receive in standard of care or a hyper-invasive resuscitation that includes mechanical chest compressions, intra-arrest nasal cooling, and early ECLS invasive assessment. The study aims to achieve ECMO support within 60 minutes and recruit 170 patients. The primary outcome is composite of survival with good neurological outcome at 6 months (Clinical Performance Category of 1-2). The study team is activated as soon as the Emergency Medical Services start to give CPR telephone advice.

**Table 1** Other studies examining ECPR in patients suffering OHCA

Study name	Status	Country	Site of ECPR	Technique	Minimum conventional CPR	Target ECPR time
RECA	- a	Germany	Pre-hospital	Percutaneous	- a	- a
CAREECMO	In set up	France	In hospital	Percutaneous	10 min	-
ACPAR2	Recruiting	France	Pre-hospital	Cut-down	20 min	<30 min
CHEER2	Recruiting	Australia	In hospital	Percutaneous	29 min	Start<45
CHEER3	In set up	Australia	Pre-hospital	Percutaneous	30 min	<45 min
EROCA	In set up	USA	In hospital	Not defined	1 shock b	<60 min
ECPB4OHCA	Recruiting	Austria	In hospital	Percutaneous	15 min	-
Prague OHCA	Recruiting	Czech Rep.	In hospital	Percutaneous	5 min	<60 min
Sub30	In set up	UK	Pre-hospital	Percutaneous	20 min	<30 min

a Details not known

b Or one rhythm analysis if a shock is not indicated

#### 4.5 Rationale for the Sub30 study

The Sub30 will investigate the technical and logistical feasibility of instituting pre-hospital ECPR within 30 minutes of collapse for selected patients in a geographical sector of Greater London. It will achieve this through a unique collaboration between the primary emergency dispatch and response services (London Ambulance Service NHS Trust, LAS), pre-hospital practitioners (LAS and London Air Ambulance) and clinicians in ECMO (Barts Health NHS Trust).

A target of thirty minutes to achieve ECMO flow is less than in published series to date. This can be achieved by:

- integration into an established pre-hospital emergency response services that aggressively pursues ROSC through optimised ALS

- immediate deployment of an ECPR-capable cardiac arrest team as a primary resource, as opposed to delayed secondary deployment. Dispatch will be done by the established Advanced Paramedic Practitioner (APP) desk of LAS, with the objective to reach the patient within 8-10 minutes of the 999 call.
- early placement of guide-wires into the femoral vessels during on-going conventional CPR, a procedure with low complication risk that does not commit the team to ECPR but will minimise the delay to ECPR support if conventional resuscitative techniques are not successful within 20 minutes
- facilitated guide-wire placement through real-time wireless ultrasound delivered to the operator through augmented reality smart glasses

Some OHCA are irreversible in nature and ECPR would not provide benefit to these patients. The ECPR team will not be task fixated on providing ECPR, but also supportive of the APP primary responders and provide ECPR only in settings of refractory cardiac arrest that fulfils the study criteria, that have been chosen based on best available evidence to identify those patients in whom ECPR is likely to be of benefit.

If pre-hospital ECMO is feasible within 30 minutes of chest compressions starting, then a larger randomised controlled study of clinical and cost effectiveness is merited. Optimisation of the delivery of ECPR is vital, prior to a controlled study, in order to maximise any potential benefits for patients. Data from Sub30 will inform the design of such studies enabling an estimation of the size of any potential outcome benefits and the likely affordability for a healthcare service. Ideally studies would be international and multi-city to understand the generalisability of pre-hospital ECMO to other urban and non-urban environments.

#### 4.6 Risks / benefits

The potential benefits relate to the restoration of blood flow to vital organs preventing or reducing neurological injury, renal failure, liver failure and cardiac failure. ECPR may also enable a patient to undergo coronary angiography and intervention whilst still in “cardiac arrest”. These may all translate to more patients surviving and survivors having better neurological outcomes.

The potential risks to participants are:

- vascular damage during cannulation. This will be mitigated by the use of ultrasound to guide the operator.
- bleeding. This is related to the administration of anticoagulants to prevent clotting in the extracorporeal circuit. Anticoagulation will be monitored closely during the study. Bleeding is common in the context of ECMO.
- local infection. This may be greater due to the procedure occurring outside the confines of a procedure room in a hospital. The risk of infection will be mitigated by using chlorhexidine skin preparation, allowing it to dry, large drapes to maximise the sterile field and prevent inadvertent contamination a single dose of prophylactic antibiotic directed against common skin commensal organisms.
- individuals, who would have previously died, surviving with neurological impairment

### 5. Study objectives

The study aims to test the hypothesis that a system that overcomes the logistical and technical barriers to minimise the collapse-to-ECPR interval and combines an ECMO team with advanced pre-hospital practitioners can establish patients in refractory cardiac arrest with ECMO flow (>50% target) within 30 minutes of collapse.

#### 5.1 Primary objective

The primary objective of the study is to assess the ability of an advanced ECMO capable resuscitation team to establish patients on ECPR within 30 minutes of collapse.

## 5.2 Secondary objectives

The secondary objectives of the study are to assess the logistics of delivering a definitive clinical study of the efficacy of pre-hospital ECPR in terms of:

- the logistics of delivering the study including potential recruitment rates
- the safety of delivery of pre-hospital ECPR
- the survival and neurological outcome of patients included in the feasibility study
- the logistics of collecting data regarding resources used and the health economics

## 5.3 Primary outcome

The primary endpoint is the proportion of patients successfully established with pre-hospital ECPR within 30 minutes of collapse. The time of collapse will be defined as the time the call to the emergency services commences or the time that a patient was witnessed to suffer a cardiac arrest if this happens in front of the emergency services.

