## 6. Study population

### 6.1 Inclusion criteria

Male or female patients with a known or visible age of 18 to 65 years who:

- have a witnessed out-of-hospital cardiac arrest
- a presumed cardiac aetiology to their cardiac arrest
- receive bystander chest compressions within 3 minutes
- remain in cardiac arrest at 20 minutes following collapse or fail to sustain ROSC in the pre-hospital setting

Out-of-hospital cardiac arrest encompasses both those who arrest prior to the emergency services being called and those who are witnessed to arrest by the emergency services. For the purpose of this study patients who suffer their first cardiac arrest whilst in transit to hospital will not be included.

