## 7.4 Patient identification / ECPR Team activation

On study days, the ECPR team will be active in a fast response blue light emergency response car provided by London's Air Ambulance. They will have no other clinical or non-clinical duties. On study days, the team will assemble at the Royal London Hospital and perform challenge/response checks on their equipment and vehicle. Once complete they will inform control that they are active and available. At various points in the day the team will be based in geographical areas where London Ambulance Service have attended the most cardiac arrests historically. At the end of the shift the team will inform control that they are standing down.

The team will be activated by the Advanced Paramedic Practitioner (APP) desk in the Emergency Operations Centre at London Ambulance Service. This desk screens in real time all calls to the emergency services that may be a cardiac arrest and dispatch additional APPs to the scene. They listen in on all calls where it is indicated on the pre-triage questions, asked by the call handler, that the patient is not breathing or has abnormal breathing. In addition, they screen calls as requested by the dispatchers. Their clinical experience at listening to calls will enable the LAS sit to identify trial subjects and dispatch the ECPR team as an additional emergency response within 2-3 minutes of the emergency call being placed. They will task the ECPR team if the estimated time of travel to the scene is 20 minutes or less.

All 'patients' for whom the team is activated will be included in the screening log. In addition to patients who are enrolled and receive ECMO, the log will indicate those people who were never assessed (as the team was stood down prior to arrival), those whose were assessed but clearly

did not meet inclusion/exclusion criteria (Section 8.2) and those in whom guidewires were inserted but were not formally enrolled in the study at the 20 minute time out (Section 8.5)

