## **8.3 ECPR Pre-hospital team roles and responsibilities**

The pre-hospital ECPR team will endeavour to achieve ROSC by delivering and supporting others in delivery of ALS to the patient. They will:

- introduce the ECPR team to any on scene healthcare resources
- manage the cardiac arrest following London Ambulance Service and Resuscitation Council ALS Guidelines
- seek ROSC by addressing reversible causes, ensuring advanced airway management and optimising resuscitation including automated mechanical compressions
- administer intravenous fluids to aid percutaneous cannulation by the ECMO team as required
- manage the pre-hospital environment and ensure team safety
- establish 360 degrees access to the patient
- establish collateral history about the patient, the collapse, and the timings of resuscitation attempts
- prepare for team timeout if cardiac arrest is refractory at 20 minutes of resuscitation by healthcare professionals

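### For arrests that no crew witnesses, the 30-minute clock starts at the emergency call, which drops any delay before the call and backdates an arrest that happens during it

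*Protocol*

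**What the plan says.** **Endpoint and origin.** Protocol 5.3: "The primary endpoint is the proportion of patients successfully established with pre-hospital ECPR within 30 minutes of collapse". The origin has two parts. The general rule is this: "The time of collapse will be defined as the time the call to the emergency services commences". The exception covers arrests that a crew sees: "or the time that a patient was witnessed to suffer a cardiac arrest if this happens in front of the emergency services".

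**Population.** Protocol 6.1 requires a witnessed arrest and says that the term "encompasses both those who arrest prior to the emergency services being called and those who are witnessed to arrest by the emergency services". It also sets two timed entry conditions: "receive bystander chest compressions within 3 minutes", with no starting point given, and "remain in cardiac arrest at 20 minutes following collapse or fail to sustain ROSC in the pre-hospital setting".

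**Dispatch and history.** Under protocol 7.4 the dispatch desk listens to calls where the caller's answers suggest that "the patient is not breathing or has abnormal breathing". Under 8.3 the pre-hospital team must "establish collateral history about the patient, the collapse, and the timings of resuscitation attempts". No section says that this history feeds the endpoint.

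**Other clocks.** Protocol 8.5 runs its 20 minutes from the start of resuscitation by a healthcare provider. SAP 3.4 counts the primary endpoint's 30 minutes from the first chest compressions, as does the rationale in protocol 4.5. SAP 3.6.1 counts from collapse, which the SAP does not define.

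**The concern.** The hypothesis (protocol section 5), the primary objective (5.1) and the survival bands in 4.2.1 (40-50% within 30 minutes, 30% for 30-60, 18% beyond 60) all depend on time from collapse. Arrests that no crew witnesses are timed from the call instead, and two gaps follow.

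- **Arrest before the call.** Any delay between collapse and call is left out, so the recorded interval is too short.
- **Arrest after the call starts, before a crew arrives.** This patient arrested neither before the call nor, on the ordinary reading, in front of the services. Taken literally, 5.3 assigns call start, which precedes the collapse, so the recorded interval is too long. Whether 6.1 admits such a patient is also unclear.

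The second group is foreseeable from the protocol. A call about abnormal breathing may concern a patient not yet in arrest, and there is time for an arrest before help arrives: the ECPR team aims to arrive 8-10 minutes after the call (4.5) and can be tasked at up to 20 minutes' travel (7.4).

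At stake is whether the feasibility figure that is meant to justify a larger randomised study measures the interval it is named for.

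**Working it through.** The plan has no figure to reproduce: six patients were chosen without a power calculation, and no test is planned (protocol 10.1; SAP 3.7, 3.8). The check is arithmetic on the clock.

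**Inputs.** From the documents: the 30-minute threshold and six patients. Assumed, because the documents give none: the offset d between collapse and call.

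**Formula.** True collapse-to-flow = recorded call-to-flow + d. Here d > 0 is a delay before the call, and d < 0 is an arrest |d| minutes into the call.

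| d (assumed, min) | True interval when 30 is recorded | Recorded time that equals a true 30 |
|---|---|---|
| +1 | 31 | 29 |
| +2 | 32 | 28 |
| +3 | 33 | 27 |
| +5 | 35 | 25 |
| -1 | 29 | 31 |
| -2 | 28 | 32 |
| -3 | 27 | 33 |

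**Single patients.**
- Collapse 3 minutes before the call, flow at call + 29: recorded 29, a success; true 29 + 3 = 32, a failure.
- Arrest at call + 6, flow at call + 34: recorded 34, a failure; true 34 - 6 = 28, a success.

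**Effect on the proportion.** One patient in six is 1/6 = 16.7 points. For example, 3/6 = 50% (exact 95% limits 12-88%) becomes 4/6 = 67% (22-96%). SAP 8.1.1 uses the treated population, which SAP Table 3 shows as N=6. The same table counts cannulation within 30, 45 and 60 minutes among candidates at the time-out, who may be more numerous; the step would then be smaller.

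**Sensitivity, purely illustrative.** Suppose call-to-flow times are normal with mean 30 minutes. The share within a true 30 minutes is then Φ((30 - d - 30)/SD).

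| Every patient shifted by d | SD 5 | SD 8 |
|---|---|---|
| 0 | 50% | 50% |
| +1 | 42% | 45% |
| +2 | 34% | 40% |
| +3 | 27% | 35% |
| -2 | 66% | 60% |
| -3 | 73% | 65% |

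A real cohort would mix signs and sizes. The table shows only that shifts of 1 to 3 minutes matter if flow times cluster near the threshold.

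**The case against.** **Call start is objective and openly stated.** Protocol 13.2 has clocks, including the dispatch desk's, checked against a time server; a bystander's estimate cannot be checked in that way. This stands, and it is the reason to keep call start as the main origin for arrests before the call.

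**The study is small and descriptive.** No test depends on the cut-off, and the separate 31-45 minute count would show a recorded 34 minutes as a near miss. This partly stands. It does not reveal a recorded 29 that was really 32.

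**The two errors have opposite signs.** True, so net bias cannot be claimed. But each patient is classified individually, and nothing makes the errors cancel among six.

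**'In front of' the services might include the call handler.** That reading would time an arrest during the call correctly. The text does not say so.

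A reader might also infer more than the documents support:

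- *That collapse is always set to the call.* Crew-witnessed arrests are timed from the arrest.
- *That the 3-minute compression criterion runs from the wrong moment.* Section 6.1 states no starting point. Counting from the call borrows the endpoint's definition; the team assesses entry on scene and takes the collapse history, so actual collapse is an equally natural reading.
- *That the error uses up a fixed share of a 10-minute margin between time-out and target.* The time-out in 8.5 runs on a different clock, so the two times cannot simply be subtracted.
- *That the reported result will certainly be a call-to-flow time.* SAP 3.4 uses yet another origin.

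**Conclusion.** The point holds for arrests not witnessed by the emergency services. For them call start is a proxy that shortens the interval by any delay before the call and lengthens it for an arrest between call start and crew arrival. That last group has no timing rule of its own in 5.3 and is not named in 6.1. No other section corrects either error, although the collapse history is already collected.

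Neither the size of the offsets nor the frequency of arrests during the call is in the documents, and the net direction is unknown. What can be said is that one patient reclassified at 30 minutes moves the proportion by about 17 points if the denominator is six.

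The origin is also unsettled across the documents: call or witnessed arrest (protocol 5.3), first compressions (protocol 4.5, SAP 3.4), and undefined collapse (SAP 3.6.1). The SAP was written from protocol version 2.0 of October 2018, which may explain part of this but does not settle it. For the entry rules, the supportable finding is limited: the 3-minute criterion has no stated origin, and the 20-minute clocks in 6.1 and 8.5 differ.

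**What to change.** 1. **Protocol 5.3 and 6.1.** Add a timing rule for an arrest between call start and crew arrival: the time at which the collapse is reported on the emergency call record where available, otherwise the witness-reported time. State in 6.1 whether this group is included.
2. **Protocol 5.3 and SAP 8.1.1.** Keep call start as the main origin for arrests before the call, but describe that result as call to ECMO flow. Pre-specify a second descriptive presentation using the witnessed collapse time gathered under protocol 8.3.
3. **SAP 3.4 and 3.6.1.** Reconcile both with protocol 5.3 so that the primary interval has one defined origin; align protocol 4.5.
4. **Entry clocks.** State the starting point of the 3-minute criterion, and reconcile the 20-minute clocks in protocol 6.1 and 8.5. Which clock applies is for the investigators to settle.

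The cost is wording in both documents and one time field. Witness times are imprecise, which is why they are secondary for arrests before the call. The documents do not show that the call record holds a time of reported collapse, hence the fallback. The headline proportion may change slightly.
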